5. TREATMENTS

5.1. Treatments Administered

Part A (q3wk dosing): LV will be administered at a dose of 2.5 mg/kg as a 30-minute IV infusion on Day 1 of each 21-day cycle. For subjects weighing more than 100 kg, dosing will be capped at 250 mg per infusion. Any subject receiving >200 mg LV per infusion (weight >80 kg) is required to receive prophylactic G-CSF.

Part B (q1wk dosing): LV will be administered at a dose of 1.0 or 1.25 mg/kg as a 30-minute IV infusion on Day 1, Day 8, and Day 15 of each 21-day cycle. The maximum dose will be 200 mg per infusion.

Part C (LV monotherapy or LV plus pembrolizumab combination): LV will be administered at a dose of 1.5 mg/kg (Arms 1 and 2) as a 30-minute IV infusion on Day 1 and Day 8 but not Day 15 of each 21-day cycle (2q3wk). The maximum dose will be 200 mg per infusion. For Arm 3, LV will be administered at a dose of 1.25 mg/kg as a 30-minute IV infusion on Day 1, Day 8, and Day 15 of each 21-day cycle (q1wk). The maximum dose will be 200 mg per infusion. For Arm 2 and Arm 3, pembrolizumab will be administered at a dose of 200 mg approximately 60–90 minutes after LV as a 30-minute IV infusion on Day 1 of each 21-day cycle (q3wk).

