5.2.4. Dose Modifications

5.2.4.1. Part A (q3wk dosing)

Dose modification guidelines for LV q3wk treatment-associated toxicity are described in [Table 9](#). The maximum doses after modifications are:

- 200 mg for subjects reduced to 2.0 mg/kg
- 150 mg for subjects reduced to 1.5 mg/kg

Table 9: Q3wk LV dose levels

Dose Level	Dose	Maximum Dose
Starting dose	2.5 mg/kg	250 mg
-1	2.0 mg/kg	200 mg
-2	1.5 mg/kg	150 mg

[Table 10](#) describes dose modifications for LV treatment-associated toxicity.

Doses reduced for LV-related toxicity should not be re-escalated.

If a subject has a clinically significant, unresolved AE on Day 1 of C2 or beyond, the start of the cycle may be delayed for up to 14 days. Delays of >14 days must be approved by the medical monitor.

In the event a subject is unable to tolerate their dose level, additional treatment cycles (C2 or later) may be administered at a lower dose level upon approval by the medical monitor.

Table 10: Dose modifications for LV-associated toxicity (Part A; q3wk dosing)

Toxicity	Grade 1	Grade 2	Grade 3	Grade 4
Peripheral neuropathy ^a	Continue at same dose level	Withhold until toxicity resolves to \leq Grade 1; then resume treatment at the next lower dose level	Withhold until toxicity resolves to \leq Grade 1, then resume treatment at the next lower dose level	Discontinue treatment
Non-hematologic ^a (except peripheral neuropathy and hyperglycemia)	Continue at same dose level	Continue at same dose level	Withhold dose until toxicity is \leq Grade 2 or has returned to baseline, then resume treatment at same dose level ^b	Withhold dose until toxicity is \leq Grade 2 or has returned to baseline, then reduce dose to the next lower dose level and resume treatment, or discontinue at the discretion of the investigator ^{b,c}
Hematologic ^a	Continue at same dose level	Continue at same dose level	Withhold until toxicity resolves to \leq Grade 2 or baseline ^{d,e} . For neutropenia, strongly consider G-CSF support , then resume treatment at the same dose level. Prophylactic G-CSF support should be strongly considered for subsequent cycles. (See Appendix G)	Withhold until toxicity resolves to \leq Grade 2 or baseline ^{d,e} . For neutropenia, strongly consider G-CSF support , then resume treatment at the same dose level. Prophylactic G-CSF support is required for all subsequent cycles. If Grade 4 neutropenia recurs despite G-CSF support, consider dose reduction to dose level -1 or discontinuation. (Appendix G)

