Febrile neutropenia ^a			G-CSF support is required for treatment of febrile neutropenia. Withhold until febrile neutropenia resolves and neutrophil count returns to \leq Grade 2 or baseline then resume treatment at the same dose level. Prophylactic G-CSF is required for all subsequent cycles. If febrile neutropenia recurs despite G-CSF factor support, consider dose reduction to dose level -1 or discontinuation.	
Hyperglycemia	Hold for blood glucose >250 mg/dL or >13.9 mmol/L. Resume treatment once elevated blood glucose has improved to ≤ 250 mg/dL or ≤ 13.9 mmol/L and subject is clinically and metabolically stable (see Section 5.6 for detail).			

Note: For subjects weighing ≥ 100 kg, dosing will be based on 100 kg for these individuals with a maximum calculated dose of 250 mg per infusion when dosed at 2.5 mg/kg.

a Only 2 dose reductions are allowed. Additional toxicities should be managed with dose delays

b Subjects who develop Grade 3 or 4 electrolyte laboratory abnormalities may continue study treatment without interruption if a management plan consistent with institutional practice and regular monitoring are put in place

c Treatment should be discontinued for subjects who experience Grade 4 infusion-related reactions

d Support with blood product transfusions allowed per institutional standard of care

e Subjects who develop Grade 3 or 4 lymphopenia may continue study treatment without interruption

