9.3.8.1. Extent of Exposure

Duration of treatment, number of cycles, total dose, and dose intensity will be summarized. Dose modifications, including dose delay, dose reduction, and unplanned dose adjustment, will be summarized. Details will be provided in the SAP.

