1 INTRODUCTION

This document outlines the statistical methods to be implemented within the scope of Protocol SGNLVA-005, entitled “Open-Label Phase 2 Study of Ladiratuzumab Vedotin (LV) for Unresectable Locally Advanced or Metastatic Solid Tumors”, Original version dated 22Apr2019. Results of the proposed analyses will become the basis of the clinical study report for this protocol.

The purpose of this plan is to provide specific guidelines from which the analysis will proceed. All planned analyses specified in this document will be performed. Any changes to this plan, in the form of “post hoc” or “data driven” analyses will be identified as such in the final clinical study report (CSR). Any changes will either be reflected in amendments to this plan before the database lock or specifically documented in the CSR.

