3 STUDY DESIGN

This global, open-label, multicenter trial is designed to assess the activity, safety, and tolerability of LV monotherapy for the treatment of solid tumors. Subjects with the following advanced solid tumors will be enrolled:

Cohort 1: SCLC

Cohort 2: NSCLC-squamous

Cohort 3: NSCLC-nonsquamous

Cohort 4: HNSCC

Cohort 5: esophageal squamous cell carcinoma (esophageal-squamous)

Cohort 6: gastric and gastroesophageal junction (GEJ) adenocarcinoma

Interim futility analyses will be performed separately for each cohort after at least 12 subjects of a given cohort have been treated and are efficacy evaluable post-baseline (Error! Reference source not found.). Enrollment to each cohort may be held after 12 subjects for interim futility analysis of the respective cohorts. The Bayesian predictive probability approach will be used to determine the futility criteria. At the time of each interim analysis, the predictive probability of success (PPoS) will be calculated. A PPoS <10% indicates that it is unlikely the objective response rate (ORR) will be better than the response rate of current standard of care at the end of the study given the interim result. Based on efficacy and safety data, together with the PPoS, a cohort may be stopped early by the sponsor.

In all subjects, LV will be administered by IV infusion at a dose of 2.5 mg/kg on Day 1 of each 21-day cycle. Dosing may not exceed 250 mg per infusion. An individual's dose may be modified based upon treatment-related adverse events (AEs). Tumor assessment according to Response Evaluation Criteria in Solid Tumors version 1.1 (RECIST v1.1) will be performed every 6 weeks for the first 12 months and then every 12 weeks thereafter. Objective responses will be confirmed with repeat scans 4-6 weeks after the first documentation of response.

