6.4 Treatment Administration

Treatment administration will be summarized with descriptive statistics using the safety analysis set. Summaries may include but are not limited to the following:

- Duration of treatment (in weeks), which is defined as time from the first study dose to the earliest of 21 days after the last study dose, EOT visit, death date or start date of subsequent anticancer therapy if applicable.
- Number of cycles per patient

- Number and percentage of patients who were treated at each cycle
- Cumulative doses, which is defined as sum of the actual dose across all cycles.
- Average dose per cycle
- Absolute dose intensity (ADI), which is defined as the actual dose in mg/kg per week that a patient received over the entire treatment period. That is, $ADI = \frac{\text{Cumulative doses}}{\text{treatment period in weeks}}$, where treatment period is defined as time from the first study dose to 21 days after the last study dose $[(\text{last dose date} + 21) - \text{first dose date}] / 7$ regardless of death date.
- Relative dose intensity (RDI), which is defined as the ADI divided by the intended dose intensity (IDI). That is, $RDI = \frac{ADI}{IDI} \times 100$, where IDI is defined as the intended dose (i.e., 2 mg/kg regardless of dose reduction in later cycles) in mg/kg per week.
- Number and percentage of patients whose dose was ever modified, which will be summarized by modification type (delay, reduction, unplanned dose adjustment), cycle and overall (i.e., overall drug administrations for a patient). The number and percentage of doses that were modified may also be summarized.

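### SAP 6.4 sets the relative dose intensity denominator at 2 mg/kg, but SAP 3 doses all subjects at 2.5 mg/kg every 21 days, so full on-time dosing does not read 100%

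*SAP*

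**What the plan says.** SAP 6.4 builds RDI in two steps. ADI is the cumulative dose in mg/kg divided by the treatment period in weeks, where the period runs from the first dose to 21 days after the last dose. RDI is 100 times ADI over IDI, "where IDI is defined as the intended dose (i.e., 2 mg/kg regardless of dose reduction in later cycles) in mg/kg per week". Because later reductions are ignored, the 2 mg/kg serves as a starting-dose reference.

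SAP 3 describes the regimen: "In all subjects, LV will be administered by IV infusion at a dose of 2.5 mg/kg on Day 1 of each 21-day cycle". It also caps each infusion at 250 mg. SAP 1 ties the plan to the protocol's "Original version dated 22Apr2019", so both statements fall within the SAP's own scope.

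The current protocol gives the same q3wk dose for Part A in Section 5.1: "LV will be administered at a dose of 2.5 mg/kg as a 30-minute IV infusion on Day 1 of each 21-day cycle". In Section 5.2.4.1, 2.0 mg/kg appears only as dose level -1 of Table 9, with the maximum dose after modification given as "200 mg for subjects reduced to 2.0 mg/kg".

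**The concern.** RDI should show how much of the planned dose intensity was delivered, and a reader takes 100% to mean full doses on schedule. With the denominator as written it does not mean that. On the natural reading, a subject who has been reduced or delayed can still show 100% or more, so the summary would make delivery of the q3wk regimen look more complete than it was. The two SAP sections cannot both describe the intended dose. Nothing in the text suggests a redaction or an extraction gap at the figure in SAP 6.4.

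**Working it through.** **Inputs.** Intended dose in the denominator: 2 mg/kg (SAP 6.4). Dose and schedule: 2.5 mg/kg every 21 days, at most 250 mg per infusion (SAP 3). The ADI, RDI and treatment-period formulas are from SAP 6.4. For the examples, protocol 5.2.4.1 says of an unresolved adverse event on Day 1 of Cycle 2 or later that "the start of the cycle may be delayed for up to 14 days", and Table 10 footnote a says "Only 2 dose reductions are allowed". The six-cycle course is my choice for illustration.

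**Formulas.**
- Weeks = [(last dose date + 21) − first dose date] / 7. For n on-time cycles this is 3n weeks.
- ADI = cumulative mg/kg / weeks.
- RDI = 100 × ADI / IDI.

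**Full on-time dosing, any n.** ADI = 2.5n / 3n = 0.8333 mg/kg/week.
- 2 mg/kg read as per 21-day cycle: IDI = 2/3 = 0.6667, so RDI = 0.8333 / 0.6667 = 125.0%.
- 2 mg/kg read literally as per week: IDI = 2, so RDI = 0.8333 / 2 = 41.7%.
- IDI from the SAP 3 regimen: 2.5/3 = 0.8333, so RDI = 100.0%.

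The per-cycle reading is the natural one, because ADI itself rests on a 21-day interval. Neither reading of the 2 mg/kg gives 100% for a subject below the cap.

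**Examples on the per-cycle reading, subject not affected by the cap, six doses.**

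| Course | mg/kg | Weeks | ADI | RDI, IDI 0.6667 | RDI, IDI 0.8333 |
|---|---|---|---|---|---|
| 2.5 throughout, on time | 15.0 | 18 | 0.8333 | 125.0% | 100.0% |
| 2.5, 2.5, 2.0, 2.0, 1.5, 1.5, on time | 12.0 | 18 | 0.6667 | 100.0% | 80.0% |
| 2.5, then 2.0 five times, on time | 12.5 | 18 | 0.6944 | 104.2% | 83.3% |
| 2.5 throughout, one 14-day delay | 15.0 | (105+14+21)/7 = 20 | 0.7500 | 112.5% | 90.0% |
| 2.5 throughout, two 14-day delays | 15.0 | (105+28+21)/7 = 22 | 0.6818 | 102.3% | 81.8% |

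**Ratio.** ADI cancels, so RDI as written over RDI against 2.5 mg/kg is 0.8333 / 0.6667 = 1.25 for every subject, whatever the weight.

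**Level above 100 kg.** Here the cap matters if mg/kg is taken on actual weight. At 110 kg, full dosing is 250/110 = 2.27 mg/kg, which reads 113.6% against 2 mg/kg and 90.9% against 2.5 mg/kg. At 125 kg it is 2.0 mg/kg, which reads 100% and 80%. SAP 6.4 does not say which weight converts mg to mg/kg.

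**The case against.** The case for leaving this alone is that very little hangs on it. SAP 6.4 lists RDI among summaries that may be produced. The protocol's requirement in Section 9.3.8.1 is "Duration of treatment, number of cycles, total dose, and dose intensity will be summarized", and ADI supplies the dose intensity without using the disputed figure. Delays and reductions are tabulated separately, so a modified subject stays visible. Values above 100% would themselves prompt a question. In the current design the q3wk regimen is Part A only, up to 72 of about 414 subjects. The protocol also says the SAP will be finalized before database lock. All of this stands and fixes the severity. It does not make the definition right, since anyone who programs SAP 6.4 as written gets a wrong RDI.

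Three stronger readings are tempting and not supported:
- A reader might infer that every fully dosed subject shows 125%. That needs the per-cycle reading and a subject not affected by the cap. The 1.25 ratio is general; the 125% level is not.
- A reader might infer that every RDI table must be rebuilt from the dosing records. Changing the constant alone is a flat rescale by 2/2.5 = 0.8. A rerun is needed only if a cap or weight convention is added.
- A reader might extend the point to the weekly and combination regimens of Parts B and C. This SAP is written to the original protocol and does not describe them, so the contradiction shown is confined to q3wk.

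**Conclusion.** The point holds as an internal inconsistency in the SAP: Section 6.4 uses 2 mg/kg as the intended dose, Section 3 states 2.5 mg/kg for all subjects, and no text accounts for the difference. Taking 2 mg/kg as per 21-day cycle, an RDI of 100% corresponds to 80% of the dose intensity in SAP 3. Taken literally per week, the error runs the other way.

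Severity is minor. Only an optional descriptive summary is affected. ADI, the confirmed ORR, the futility rule and the sample size do not use IDI. The documents give no ground for inferring that any efficacy or stopping conclusion is at risk.

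**What to change.** Reconcile SAP 6.4 with SAP 3, checking both against protocol 5.1 and Table 9. Replace the hard-coded figure with a reference: for q3wk, IDI is the protocol-assigned starting dose per 21-day cycle in mg/kg, divided by 3 weeks. Stating the per-cycle basis also removes the weekly ambiguity.

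That change alone makes full on-time dosing read 100% only where the cap does not bite. With actual weight, the 110 kg subject above would still show 90.9%. If 100% is wanted above 100 kg too, the SAP should either apply the 250 mg cap to the intended dose or use the capped dosing weight for both actual and intended dose. This is a separate, optional clarification.

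The cost is one definition and one derivation in the analysis programs, with no new data. Any RDI output already produced on the per-cycle reading is multiplied by 0.8 if only the constant changes. It is rerun from the dosing records only if the cap convention changes as well.

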6.5 Efficacy Analyses

All efficacy endpoints will be analyzed by cohort and total using the FAS. In addition, the objective response rate and disease control rate will be analyzed using the EE set.

6.5.1 Primary Endpoint

6.5.1.1 Confirmed Objective Response Rate (ORR)

The primary endpoint of this study is the confirmed ORR per investigator assessment. The confirmed ORR is defined as the proportion of patients who achieve a confirmed CR or PR according to RECIST v1.1 (Eisenhauer 2009). Patients who do not have at least two post-baseline response assessments (initial response and confirmation scan) will be counted as non-responders. Confirmation means a PR is followed by a PR or CR at least 4 weeks later, or a CR is followed by a second CR at least 4 weeks later.

The confirmed ORR of each cohort and its exact 2-sided 90% CI will be calculated.

This endpoint will also be summarized by the subgroups defined in Section 0.

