9.2. Study Endpoint Definitions

9.2.1. Confirmed ORR

Confirmed ORR is defined as the proportion of subjects who achieve a confirmed CR or PR according to RECIST v1.1 as assessed by the investigator. Subjects who do not have at least 2 post-baseline response assessments (initial response and confirmation scan) will be counted as non-responders.

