APPENDIX H. RECIST VERSION 1.1

Response Evaluation Criteria in Solid Tumors

Term	Definition
Complete response (CR)	Disappearance of all target lesions. Any pathological lymph nodes must have reduction in short axis to <10 mm.
Partial response (PR)	A $\geq 30\%$ decrease in the sum of diameters of target lesions, taking as reference the baseline sum diameters.
Progressive disease (PD)	At least a 20% increase in the sum of diameters of target lesions, taking as reference the smallest sum on study (this includes the baseline sum if that is the smallest on study). In addition to the relative increase of 20%, the sum must also demonstrate an absolute increase of at least 0.5 cm. The appearance of one or more new lesions is also considered progression.
Stable disease (SD)	Neither sufficient shrinkage to qualify for PR nor sufficient increase to qualify for PD, taking as reference the smallest sum diameters while on study.
Measurable lesion	Must be accurately measured in at least one dimension (longest diameter in the plane of measurement is to be recorded) with a minimum size of 10 mm by CT scan (CT slice thickness no greater than 5 mm).

From RECIST v1.1 ([Eisenhauer 2009](#))

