5.4.2 Best Response

The determination of antitumor activity will be based on objective response assessments made by the investigator according to the RECIST v1.1 (Eisenhauer 2009). Only response assessments on or prior to start date of any new anticancer therapy will be considered for best response. The patient's best response will be the best demonstrated response to date that has been confirmed, when confirmation is required (i.e. for PR and CR only). The patient's best response will be used in determining the ORR.

A response (CR or PR) will be considered confirmed if the subsequent disease assessment conducted no earlier than 4 weeks after the initial response still shows CR or PR. A patient will have a best response of SD if there is at least one SD assessment (or better) ≥ 5 weeks after the start of treatment and the patient does not qualify for confirmed CR or PR. RECIST v1.1 outlines scenarios for best overall responses when confirmation of CR and PR is required.

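### SAP 5.4.2 and 6.5.1.1 give contradictory confirmation rules for the primary endpoint: a CR followed only by a PR is a confirmed response under one and not under the other

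*SAP*

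**What the plan says.** SAP 5.4.2 (Best Response) treats CR and PR alike. A response is confirmed if "the subsequent disease assessment conducted no earlier than 4 weeks after the initial response still shows CR or PR", and the section adds that the patient's "best response will be used in determining the ORR".

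SAP 6.5.1.1 (Confirmed Objective Response Rate) defines the primary endpoint and gives its own rule, with a separate limb for each kind of response. For a PR: "Confirmation means a PR is followed by a PR or CR at least 4 weeks later". For a CR, confirmation requires that "a CR is followed by a second CR at least 4 weeks later".

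Neither section refers to the other's rule or says which governs. Three other places bear on the question:

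- Protocol 9.2.1 sets a minimum number of scans ("Subjects who do not have at least 2 post-baseline response assessments (initial response and confirmation scan) will be counted as non-responders") but says nothing about which sequences qualify.
- SAP 5.4.2 points outward: "RECIST v1.1 outlines scenarios for best overall responses when confirmation of CR and PR is required". The scenarios themselves are not reproduced. Protocol Appendix H defines CR, PR, SD and PD without a confirmation rule.
- SAP section 3 gives a timing: "Objective responses will be confirmed with repeat scans 4-6 weeks after the first documentation of response". Both confirmation rules repeat only the 4-week minimum.

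**The concern.** Both rules feed the same number. A programmer who derives best response from 5.4.2 and one who codes the endpoint from 6.5.1.1 can each follow the SAP faithfully and report different confirmed ORRs for the same data. The DOR population inherits the difference, because SAP 6.5.2.2 computes DOR only for confirmed responders.

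The trial is open-label and response is assessed by the investigator. A definition left unsettled until the scans have been read may be settled with the results in view.

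**Working it through.** **1. Classify scan sequences under each section.** Assume scans 6 weeks apart (the SAP schedule for the first 12 months), so every later scan meets the 4-week minimum. Each section is applied twice: once taking the confirming scan to be the next one, and once allowing any later one.

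| Sequence | 5.4.2, next scan | 5.4.2, any later | 6.5.1.1, next scan | 6.5.1.1, any later |
|---|---|---|---|---|
| PR, PR | yes | yes | yes | yes |
| PR, CR | yes | yes | yes | yes |
| CR, CR | yes | yes | yes | yes |
| CR, PR | yes | yes | **no** | **no** |
| CR, PR, PD | yes | yes | **no** | **no** |
| CR, PR, PR | yes | yes | yes | yes |
| PR, SD, PR | no | yes | no | yes |

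The CR-then-PR conflict appears on every reading. It disappears if another qualifying pair exists, as in CR-PR-PR.

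PR-SD-PR is different. If both sections are read as next scan, or both as any later scan, they agree. They part only if 5.4.2 is read strictly and 6.5.1.1 loosely. Neither section mentions an intervening SD. At 6-week spacing the second PR comes 12 weeks after the first, outside the 4 to 6 weeks in SAP section 3, but neither rule says that this upper limit binds.

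**2. Reproduce the plan's own figures.** The SAP uses two-sided 90% Clopper-Pearson limits: lower = Beta quantile 0.05 with parameters (x, n−x+1), upper = Beta quantile 0.95 with (x+1, n−x). For x = 3, 6, 9, 12 and 15 of 30 this gives (2.8, 23.9), (9.1, 35.7), (16.6, 46.5), (25.0, 56.6) and (33.9, 66.1) percent. These match the table in SAP 5.2 after rounding.

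**3. Effect of one reclassified subject on the final ORR.**
- n = 30: 1/30 = 3.3 points. For example, 5/30 = 16.7% (6.8%, 31.9%) versus 6/30 = 20.0% (9.1%, 35.7%).
- n = 12 (a Part A cohort that ends there, Protocol 9.1): 1/12 = 8.3 points.

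**4. Effect on the success criterion.** SAP section 7 calls a cohort a success if the posterior probability that ORR exceeds p0 is above 90%. No prior is stated, so one must be assumed. With Beta(a, b), the posterior after x of 30 is Beta(a+x, b+30−x). Beta(0.2, 0.8) gives PPoS of 0.25, 8.3, 36.4, 73.2, 94.4 and 99.6% for 0 to 5 responses at p0 = 10%, against 0.2, 8, 36, 73, 94 and 100% in Table 7-1. At p0 = 15% it is within about one point of the table.

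| p0 | Posterior just below cut-off | Posterior at cut-off | Cut-off range over priors tried |
|---|---|---|---|
| 10% | 0.851 at 5/30 | 0.940 at 6/30 | 5 to 6 |
| 15% | 0.868 at 7/30 | 0.941 at 8/30 | 7 to 8 |

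The priors tried were Beta(1, 1), Beta(0.5, 0.5), Beta(p0, 1−p0) and Beta(0.2, 0.8), plus Beta(0.25, 0.75) at p0 = 15%.

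**5. Effect on the interim.** The footnote to SAP Table 7-1, and to Protocol Table 20, counts unconfirmed as well as confirmed responses. Neither confirmation rule enters that count.

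**The case against.** The best argument on the other side is that the real mismatch is narrow. It needs a first response of CR, then a PR, then no further confirming scan. Appendix H limits how often that can occur: regrowth of 20% or more from the smallest sum is PD, provided "the sum must also demonstrate an absolute increase of at least 0.5 cm", and so is any new lesion. What remains is mainly small or nodal regrowth. The LV monotherapy results in Protocol 1.2.4.4 show no CR in 60 (q3wk) or 39 (q1wk) subjects, and this SAP covers q3wk monotherapy only. That stands as a reason to expect few discordant cases, with two limits. Those subjects had breast cancer, not the tumors studied here. And the combination study in Protocol 1.3.3.3 reports 2 confirmed CRs in 66, so CRs could matter more if the same text is carried into an SAP for Part C.

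It can also be said that RECIST v1.1, cited in both sections, settles the matter. The documents do not reproduce its confirmation scenarios, and a general citation does not say which of two differing SAP sentences to program. SAP section 1 does require changes to be made by amendment before database lock or documented in the CSR, which reduces the risk of an undisclosed choice. It does not say which rule applies meanwhile.

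Three stronger readings are tempting, and the documents do not support them:

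- **That one subject could cross the futility line (1 versus 2 of 12).** The interim counts unconfirmed responses, so the rules cannot change it. The 8.3-point figure applies only to a final confirmed ORR at n = 12.
- **That PR-SD-PR is a second stated contradiction.** It is an ambiguity, and becomes a conflict only if the two sections are read differently.
- **That the rules would overturn a success decision.** Success is defined for the PPoS calculation. The planned primary analysis is an estimate with an exact interval, without a formal test, and the cut-offs rest on an assumed prior.

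**Conclusion.** The contradiction is real and sits in the definition of the primary endpoint: for CR-then-PR with no other qualifying pair, the SAP cannot be followed as written. This is more than missing detail, because the two sections give opposite answers and neither yields to the other. The status of an intervening SD is a lesser, related ambiguity.

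Neither section is uniformly the stricter. Section 5.4.2 is more lenient for CR-then-PR. For PR-SD-PR, on the split reading, 6.5.1.1 is more lenient. There is therefore no conservative default to fall back on.

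The final confirmed ORR and the DOR population are affected, and the futility count is not. The size is one subject at a time, and a success conclusion could change only in a cohort already at the boundary under the assumed prior. The expectation that such cases are uncommon rests on the Appendix H progression threshold. The documents give no direct estimate of how often they occur.

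**What to change.** Keep a single confirmation rule in SAP 5.4.2 and replace the confirmation sentence in 6.5.1.1 with a cross-reference to it. In 5.4.2, before data review, state two outcomes explicitly: whether CR-then-PR counts as a confirmed response, and whether an intervening SD breaks confirmation.

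The cost is one SAP paragraph. Site conduct, imaging schedule and sample size do not change. SAP section 1 allows amendment before database lock, and Protocol 9.3 calls for a protocol amendment only when an analysis change alters site conduct.
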